3.1.2 Phase 2a

The Phase 2a portion of the study will comprise of all approximately 90 patients (including the first 6 patients assessed in the Phase 1b portion) to assess the efficacy, safety, and pharmacodynamics of CyPep-1 (20 mg Q2W) in combination with the anti-PD-1 antibody pembrolizumab (400 mg Q6W). Patients will receive IT injections of a fixed concentration of CyPep-1 Q2W beginning at Cycle 1 Visit 1. Pembrolizumab will be administered IV at a fixed dose Q6W beginning at Cycle 1 Visit 1. Each treatment cycle will be 6 weeks, and treatment will continue for a maximum of 18 cycles (108 weeks) or until the occurrence of confirmed progressive disease (PD), excessive toxicity, death, or withdrawal of consent. Patients who complete all 18 cycles, which is the Food and Drug Administration (FDA)-approved maximum duration of pembrolizumab use, may continue receiving CyPep-1 at the current dose if determined beneficial by the Investigator and following approval of the Sponsor. CyPep-1 monotherapy may proceed until the occurrence of confirmed PD, excessive toxicity, death, or withdrawal of consent.

Radiological assessments and local measurements of tumor lesion(s), according to RECIST v1.1, will be conducted and evaluated at baseline (screening) and at 8-week intervals after the first dose of CyPep-1 through the last Progression Follow-up Visit during the Follow-up Period (up to approximately 26 months after the start of treatment). Radiological assessments can be more frequent if clinically indicated. Magnetic resonance imaging (MRI) or computed tomography (CT)

are the preferred scanning procedures to be used in this study. Selection of either MRI or CT should be based on individual patient considerations and local regulations and is at the Investigator's discretion. Once selected for each patient, the same scanning procedure should be used consistently at all remaining visits. Scans will be collected and held centrally for potential central radiologic review. When radiological PD is identified by the Investigator, PD is to be confirmed by another set of scans performed approximately 4 weeks to ≤8 weeks later according to immune-RECIST (iRECIST) guidelines (Appendix D). If PD is not confirmed, study treatment will continue until progression is confirmed.

Patients who have confirmed PD or discontinue treatment for any other reason will be followed-up by phone call every 3 months for survival until the end of study (approximately 26 months after the start of treatment).

Unless death or withdrawal of consent occurs, patients who received any injection of CyPep-1 will have a Safety Follow-up Visit 30 days after the last CyPep-1 injection. If the End of Treatment (EoT) Visit occurs more than 30 days after the last dose of study treatment, the Safety Follow-up Visit will be skipped. Patients who terminate treatment prior to 18 cycles will continue to be followed for progression every 8 weeks (Q8W) from start of study treatment until the occurrence of confirmed PD as defined by iRECIST (Appendix D) or start of new anti-cancer treatment. These patients will also be followed for survival for up to approximately 26 months after the start of treatment.

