A sample size of 27 patients will produce a 2-sided exact 80% confidence interval of 34.4% to 62.0% when the sample proportion is 48% (13/27) and an interval of 38.1% to 65.5% when the sample proportion is 52% (14/27). The lower bounds are computed through an exact binomial test.

The Simon's 2-Stage Design will be used in the Phase 2 portion to determine whether CyPep-1 has sufficient anti-tumor activity to warrant further development for patients with advanced or metastatic HNSCC, melanoma, or TNBC. A true ORR ≤9% is considered insufficient to warrant further study (null hypothesis), whereas a true ORR ≥25% is considered sufficiently effective (alternative hypothesis). The number of patients in each stage and the minimum number of patients achieving objective response (CR + PR) per RECIST v1.1 needed to continue to the next stage will be determined based on the Simon's 2-Stage Design with 80% power and a 1-sided significance level of 10% for each arm separately. Based on this design, up to 16 evaluable patients will be accrued for Stage 1. If ≤1 patient of these 16 patients achieves objective response (CR + PR) per RECIST v1.1, the enrollment for the expansion cohort will terminate. Otherwise, 10 additional evaluable patients will be evaluated in Stage 2. In order to enroll the required number of evaluable patients, it is anticipated that approximately 18 and 12 patients (total of approximately 30 patients) will be enrolled into Stages 1 and 2, respectively. Upon completion of Stage 2, if >4 patients out of the total 26 evaluable patients achieve objective response (CR + PR) per RECIST v1.1, then the null hypothesis will be rejected. If the required minimum number of responses is observed prior to completion of enrollment, then the transition between the first and second stages will occur without interruption. If the minimum is not observed at the time enrollment is completed, then enrollment in the second stage will be held until the continuation criterion is met.

SITES: Approximately 35 study sites

SPONSOR:

Cytovation ASA [name]

[contact]

TABLE OF CONTENTS

Sig	gnatur	e Page .		2
Inv	estiga	ator Agi	reement	3
Sy	nopsis	S		4
Ta	ble of	Conten	its	18
Lis	st of T	ables		22
Lis	st of F	igures		23
Lis	st of A	bbrevia	ations and Definition of Terms	24
1	Intro	duction	and Background Information	27
	1.1	Precli	nical and Clinical Data Summary	27
		1.1.1	Preclinical Studies With CyPep-1	27

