3.1.1 Phase 1b

The Phase 1b portion of the study will comprise of the first 6 patients enrolled in the study to confirm the recommended CyPep-1 dose (20 mg Q2W) based on safety and tolerability observations.

Patients will receive IT injections of a fixed concentration of CyPep-1 Q2W beginning at Cycle 1 Visit 1. Pembrolizumab will be administered IV at a fixed dose Q6W beginning at Cycle 1 Visit 1. Patients must be observed for 4 hours post injection for PK monitoring on Cycle 1 Day 15. The plasma concentration-time profile of CyPep-1 and, if detectable, the derived PK parameters will be assessed.

The DLT period for the Phase 1b portion of the study will be Cycle 1 (initial 6 weeks of study treatment); see Section 3.1.1.1. After the first 6 patients have completed the DLT period, the DMC and Sponsor will review safety and tolerability data prior to the enrollment of the patients into the Phase 2a portion of the study. If \leq 2 DLTs are observed in the first 6 patients, then the recommended CyPep-1 dose will be confirmed and enrollment of the remainder of the patients should continue.

If >2 of the 6 patients develop a DLT at the recommended CyPep-1 dose level (5 mg/mL dose concentration), then the MTD of CyPep-1 will be assumed to have been exceeded and dose de-escalation will be conducted to determine the MTD. At least 6 patients will be treated at CyPep-1 dose level -1 (2 mg/mL dose concentration). If necessary, due to >2 DLTs in the dose level -1 cohort, a further reduction to dose level -2 (0.5 mg/mL dose concentration) will be performed.

Dose de-escalation will proceed according to the following rules:

- If 2 out of 6 patients develop a DLT, the MTD will be declared; or
- If >2 out of 6 patients develop a DLT, the dose will be de-escalated to the next lower dose.

The MTD will guide confirmation, by agreement of the DMC and the Sponsor, of a recommended Phase 2 dose (RP2D). The RP2D may be equivalent to the MTD or may be a dose below the MTD and will be dependent on an acceptable tolerability profile and manageable AEs.

The patients from Phase 1b will continue to the Phase 2a portion of the study. After the DMC reviews the safety data, feedback will be provided to the Sponsor regarding the further conduct of the study, see Section 3.1.2.

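### If the dose is de-escalated, the protocol's carry-over of Phase 1b patients would mix dose levels in the Phase 2a Simon decision and ORR

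*Protocol*

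**What the plan says.** Protocol Section 3.1.1 starts the first 6 patients at the 5 mg/mL concentration. If more than 2 of the 6 have a DLT, the dose goes down: "At least 6 patients will be treated at CyPep-1 dose level -1 (2 mg/mL dose concentration"), with a further step to 0.5 mg/mL if needed. The RP2D may equal the MTD or lie below it. Directly after these rules the section states: "The patients from Phase 1b will continue to the Phase 2a portion of the study". SAP Section 2.3.1 repeats the carry-over.

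Protocol Section 3.1.2 then counts all of about 90 patients in Phase 2a, "including the first 6 patients assessed in the Phase 1b portion", and describes the CyPep-1 dose there as 20 mg Q2W.

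The decision rule is in the Synopsis under Sample Size Determination. It is a Simon two-stage design with "80% power and a 1-sided significance level of 10% for each arm separately", a null ORR of 9% and an alternative of 25%. For each arm, "up to 16 evaluable patients will be accrued for Stage 1". If at most 1 of the 16 "patients achieves objective response (CR + PR) per RECIST v1.1, the enrollment for the expansion cohort will terminate". Otherwise 10 more evaluable patients follow, and more than 4 responders among 26 rejects the null.

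Protocol Section 9.1 defines the FAS as anyone who received a CyPep-1 injection. It defines the EAS by CyPep-1 on at least two treatment days, at least one pembrolizumab dose and at least one post-baseline tumor assessment. Section 9.2.1 analyses efficacy in the FAS, with the EAS as sensitivity analysis for the primary endpoint. None of these definitions mentions dose level.

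**The concern.** A two-stage rule should keep its error rates in every branch that the protocol itself foresees. If the starting dose is abandoned, the first 6 patients were treated at a level judged to exceed the MTD. Under the text as written they would still fill places among the 16 and 26 evaluable patients and enter the primary ORR.

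The result would then be a weighted average over dose levels instead of the response rate at the dose taken forward. Responses at the abandoned level could carry an inactive lower dose over a threshold, and poor results there could stop an active one. The fixed 20 mg Q2W description in Section 3.1.2 adds a direct conflict: after de-escalation it would no longer describe Phase 2a.

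**Working it through.** **Inputs from the Protocol Synopsis, Sample Size Determination.** Null ORR 0.09, alternative 0.25, one-sided limit 0.10, power 0.80, n1 = 16, stop if at most 1 response, n = 26, reject if at least 5 responses.

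**Assumptions not in the documents.** k is the number of abandoned-dose patients among an arm's 16 Stage 1 patients: 2 if the six spread evenly over three arms, 6 if all fall in one arm. q is the ORR at the abandoned dose and p the ORR at the selected dose.

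**Step 1: the stated design.** With X1 ~ Bin(16, p) and X2 ~ Bin(10, p), the rejection probability is P(X1 ≥ 2 and X1 + X2 ≥ 5).
- p = 0.09: 0.0756 (type I error). Early stopping has probability 0.91^16 + 16 × 0.09 × 0.91^15 = 0.571.
- p = 0.25: 0.803 (power). Early stopping has probability 0.063.

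The design meets its stated limits. A search over alternative designs shows that it is the minimax design for these inputs.

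**Step 2: the same bounds with mixed doses.** Now X1 = Bin(k, q) + Bin(16 − k, p), with X2 ~ Bin(10, p) as before.

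| k | q | p | P(stop at Stage 1) | P(reject null) | Compare with |
|---|---|---|---|---|---|
| 2 | 0.15 | 0.09 | 0.528 | 0.090 | 0.0756 attained, 0.10 limit |
| 2 | 0.25 | 0.09 | 0.458 | 0.115 | same |
| 6 | 0.15 | 0.09 | 0.448 | 0.123 | same |
| 6 | 0.25 | 0.09 | 0.276 | 0.223 | same |
| 2 | 0.09 | 0.25 | 0.087 | 0.759 | 0.803 |
| 6 | 0.09 | 0.25 | 0.158 | 0.650 | 0.803 |

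**Step 3: what the ORR would estimate.** The expected proportion among 26 is (k·q + (26 − k)·p)/26. For k = 6, q = 0.25, p = 0.09 it is (1.5 + 1.8)/26 = 12.7%, not 9%. For k = 6, q = 0.09, p = 0.25 it is (0.54 + 5)/26 = 21.3%, not 25%.

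**Step 4: how often the branch is reached.** P(more than 2 of 6 DLTs) = 1 − Σ(x = 0 to 2) C(6, x) d^x (1 − d)^(6−x) for a true DLT rate d:

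| d | 10% | 20% | 25% | 33% | 40% |
|---|---|---|---|---|---|
| P(trigger) | 0.016 | 0.099 | 0.169 | 0.313 | 0.456 |

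This covers the DLT trigger only. An RP2D set below the starting dose without that trigger would come on top, and the documents give no basis for its probability.

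**Step 5: conditional and joint risk.** The figures in Step 2 are conditional on de-escalation. At d = 25%, q = 0.25 and p = 0.09, the added joint probability of de-escalating and wrongly rejecting is 0.169 × (0.223 − 0.076) = 0.025 for k = 6, and 0.169 × (0.115 − 0.076) = 0.007 for k = 2.

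**The case against.** **The protocol never says that patients from an abandoned dose stay in the efficacy counts.** A reader might infer an express rule to that effect, and there is none. Section 3.1.2 is written for the confirmed-dose case, and a de-escalation would probably bring an amendment. This stands as a limit on the wording. But the carry-over sentence in Section 3.1.1 follows the de-escalation and RP2D rules and carries no condition, and the analysis sets ignore dose. Applying the text as written in that branch mixes dose levels.

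**The text available is incomplete.** Protocol Sections 5.1, 5.2 and 9.2.4 and Table 8 (dose cohorts) are listed in the contents but not visible. The absence of a dose criterion can be confirmed only for the text shown. That text includes the analysis sets, the efficacy analysis and the Synopsis version of the Simon rule.

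**De-escalation may be unlikely.** Protocol Table 5 shows no severe CyPep-1-related event among 3 + 5 + 6 = 14 patients in the earlier study. That sample is small, and the text shown does not establish that it covers the combination. The joint risks in Step 5 are modest.

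**Early toxicity stops are partly handled.** One might infer that they would count as failures in the Simon rule. The earliest ones would not be evaluable under the EAS criteria. Later Cycle 1 stops could still count, and in the FAS patients without post-treatment assessments are non-responders.

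**The study is described as hypothesis-generating, with a sample size set on practical grounds.** It still states a per-arm decision rule with error limits, so that rule should hold in each planned branch.

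**Conclusion.** The point holds as a conditional gap in the protocol. If the dose is de-escalated, or the RP2D is set below the starting dose, the per-arm Simon decision and the ORR would mix dose levels as written, and Section 3.1.2 conflicts with Section 3.1.1 on the Phase 2a dose.

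The size depends on the arm split and on the ORR at the abandoned dose, neither of which the documents give. With two such patients per arm the effect is small: one of the two false-positive scenarios stays inside the 10% limit and the other is slightly above it. With all six in one arm it is material in both directions. The sign follows from whether response at the abandoned dose is higher or lower than at the selected one.

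Two stronger readings fail. One is that pooling Phase 1b patients is wrong in itself: if the starting dose is confirmed, no dose levels are mixed. The other is that the reported results are compromised: SAP Section 1 limits the SAP to Phase 1b because the study was terminated, and the SAP plans neither a Simon decision nor an ORR analysis per RECIST v1.1.

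**What to change.** In Protocol Sections 3.1.2, 9.1 and 9.2.1 and in the Simon text, add: *Only patients treated at the confirmed RP2D count toward the 16 and 26 evaluable patients and the primary ORR. Patients treated at any other dose level are summarised separately by dose level and remain in the Safety Analysis Set.* Section 9.1 has to change as well, because the present FAS definition would otherwise contradict the new ORR denominator.

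Reconcile the fixed-dose description of Phase 2a in Section 3.1.2 with the de-escalation and RP2D rules in Section 3.1.1. No dose is proposed here.

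If the starting dose is confirmed, the change costs nothing. Otherwise 6 patients (one abandoned level) to 12 (two levels at 6 each) are reported separately. Their places can be refilled, giving 90 + 6 = 96 to 90 + 12 = 102 enrolled and keeping the 0.0756 and 0.803 of the stated design. In that case, say how refilling fits with the no-replacement rule in Section 4.5.3. The alternative is to leave the places empty and restate the affected arm's attained power for the smaller count.

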AEs will be recorded from the time of signing the ICF until 30 days after the last dose of study treatment. All AEs that are considered serious will be monitored and recorded until 90 days (30 days if patients initiate new anti-cancer therapy) after the last dose of study treatment. Other safety assessments will be conducted as described in the Schedule of Assessments (Appendix A). The Data Monitoring Committee (DMC) will review accumulating safety data in regular intervals as per the DMC charter.

An overview of the study flow is presented in Figure 3.

Figure 3. Study Flow

The Phase 1b portion of the study will comprise of the first 6 patients enrolled in the study. After the first 6 patients have completed the DLT period (Cycle 1 [initial 6 weeks of study treatment]), the DMC and Sponsor will review safety and tolerability data prior to the enrollment of the remainder of the patients into the Phase 2a portion of the study.

DLT = dose-limiting toxicity; DMC = Data Monitoring Committee; EoT = End of Treatment; FU = follow-up; IT = intra-tumoral(ly); IV = intravenous(ly); n = number of treatment cycle; Q6W = every 6 weeks; Q8W = every 8 weeks; Screen = screening.

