4.5.1 Discontinuation of Study Treatment

A patient may be discontinued from study treatment before the end of the Treatment Period but remain in the study for safety follow-up for any of the following reasons:

- A confirmed complete response (CR) is attained, and the patient has been treated for at least 8 cycles (ie, at least 24 weeks), including 2 cycles of the combination treatment (including 2 doses of pembrolizumab) from the date when the initial CR was declared;
- Occurrence of a severe systemic hypersensitivity reaction that is uncontrolled with standard management or requires high dose steroids;
- Occurrence of necrosis, ulcerations, bleeding, or any other serious complication in healthy tissues surrounding the injected tumor;
- Occurrence of injected tumor ulcerations that do not show a healing trend in a 3-week period;
- Occurrence of any other medical condition or circumstance that exposes the patient to substantial risk and/or does not allow the patient to adhere to the requirements of the protocol;
- Any SAE, clinically significant AE, severe laboratory abnormality, intercurrent illness, or other medical condition which indicates to the Investigator that continued participation is not in the best interest of the patient;

- Pregnancy;
- Requirement of prohibited concomitant medication;
- Patient requests discontinuation of study treatment for any reason; and/or
- Patient failure to comply with protocol requirements or study-related procedures.

If a patient discontinues CyPep-1 but remains eligible to participate in the study after review by the Investigator and Medical Monitor, pembrolizumab treatment will be continued Q6W as per institutional guidelines until PD, unacceptable toxicity, or consent withdrawal by patient for a maximum of 18 treatment cycles. All assessments will continue to be performed according to the Schedule of Assessments (Appendix A).

If a patient discontinues pembrolizumab but remains eligible to participate in the study after review by the Investigator and Medical Monitor, CyPep-1 treatment will be continued Q2W until PD, unacceptable toxicity, or consent withdrawal by patient for a maximum of 18 treatment cycles. All assessments will continue to be performed according to the Schedule of Assessments (Appendix A).

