4.5.3 Discontinuation of Enrollment Criteria

Discontinuation of enrollment will occur for Phase 2a patients who meet any of the following criteria:

[figure not shown]
- Any CTCAE Grade 5 toxicity attributed to CyPep-1;
- SUSAR ≥Grade 4 CTCAE attributed to any component of the treatment combination;
- Signal of increased frequency or severity of any irAEs leading to permanent discontinuation as defined in Table 10;
- Site of injection AEs ≥Grade 4 CTCAE caused by CyPep-1 that do not revert to ≤Grade 1 in a 2 week period; or
- Any CyPep-1 related toxicity resulting in liver abnormality meeting Hy's Law criteria.

[figure not shown]
The observation of any of these criteria must trigger the immediate decision by the Sponsor to stop recruitment and organize an urgent DMC meeting, which will assess the causality of the observed AEs and the fulfillment of the discontinuation of enrollment criteria (above). The DMC will formulate a recommendation to resume recruitment, discontinue the involved cohort, or stop the study.

If a patient withdraws prematurely from the study due to the above criteria or any other reason, study staff should make every effort to complete the full panel of assessments scheduled for the EoT Visit (7 [±2] days after the last CyPep-1 or pembrolizumab administration). Withdrawal from the study will not affect or prejudice the patient's further care or treatment.

In the case of a patient lost to follow-up, attempts to contact the patient must be made and documented in the patient's medical records.

Patients who are discontinued from the study before receiving at least 1 dose of study treatment will be replaced. Patients who are discontinued from the study after receiving at least 1 dose of CyPep-1 or pembrolizumab will not be replaced. In case of pembrolizumab-related toxicity (≥Grade 2 according to the NCI CTCAE v5.0), treatment with CyPep-1 will be delayed and planned after a review by the Investigator and Medical Monitor. If CyPep-1 treatment is delayed >7 days, that dose will be omitted. After 14 days of delay, consult with the Sponsor. See Section 5.5.3.3 for management of dose toxicity.

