5.5.3 Study Drug Administration

The overall study treatment regimen is defined as IT CyPep-1 in combination with IV pembrolizumab.

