5.6.4 Documentation of Prior and Concomitant Medication Use

Medications and therapies taken within 28 days prior to the Screening Visit until the Safety Follow-up Visit will be recorded in the eCRF. All concomitant medications and changes in concomitant medications (including vitamins and minerals) will be recorded throughout the course

of the study in the eCRFs. Information recorded will include the medication name, dose, duration, and reason for taking each medication.

Medications and therapies taken specifically for the management of solid tumors prior to signing the ICF will be recorded on the Prior Medications and Therapies page of the eCRF.

All medications, including prescription and over-the-counter drugs; vitamins and minerals; and IV medications, fluids, and therapies used during the study, in addition to the study treatment (CyPep-1 and/or pembrolizumab), will be considered concomitant. All concomitant medications administered during SAEs or AEs of clinical interest (AECIs) are also to be recorded. The following concomitant medications or therapies are of clinical interest:

- Palliative medications;
- Medication for the treatment of infections, including prophylactic or pre-emptive use of anti-infective medication;
- Medication for the treatment of other reported AEs; and
- Prophylactic use of immunosuppressive medication.

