9 STATISTICS

9.1 Analysis Sets

The Full Analysis Set (FAS) will include all patients who receive an injection of CyPep-1. The FAS will be used in the analysis of efficacy and exploratory endpoints.

The Evaluable Analysis Set (EAS) will include all patients who receive an injection of CyPep-1 on at least 2 treatment days, receive at least 1 administration of pembrolizumab, and have at least 1 post-baseline tumor response assessment after the first injection of CyPep-1 (Cycle 1 Visit 1).

The Safety Analysis Set (SAS) will include all patients who receive at least 1 injection of CyPep-1 or at least 1 administration of pembrolizumab. The SAS will be the basis of safety analyses.

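### The Safety Follow-up Visit is timed from the last CyPep-1 injection, while the adverse-event window runs from the last dose of either drug

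*Protocol*

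**What the plan says.** The visit rule in Protocol Section 3.1.2 has two limits, who gets the visit and when: "patients who received any injection of CyPep-1 will have a Safety Follow-up Visit 30 days after the last CyPep-1 injection". The synopsis has the same rule. The next sentence drops the visit when EoT comes more than 30 days after the last dose, but there the clock is study treatment and not CyPep-1.

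The surrounding safety provisions use either drug:

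- Section 5.5.3: "The overall study treatment regimen is defined as IT CyPep-1 in combination with IV pembrolizumab". Section 5.6.4 likewise treats study treatment as one or both drugs.
- Section 3.1, AEs: "AEs will be recorded from the time of signing the ICF until 30 days after the last dose of study treatment". Section 8.1 agrees, and SAP Section 3.7.1 ends the TEAE period at the same point.
- Section 3.1, serious AEs: "All AEs that are considered serious will be monitored and recorded until 90 days" after the last dose of study treatment, shortened to 30 days if new anti-cancer therapy starts.
- Section 9.1, Safety Analysis Set: "all patients who receive at least 1 injection of CyPep-1 or at least 1 administration of pembrolizumab". SAP Section 3.2.2 is the same.
- Section 4.5.3, in a sentence on premature withdrawal: "EoT Visit (7 [±2] days after the last CyPep-1 or pembrolizumab administration".

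Section 4.5.1 provides for patients who stop CyPep-1 but remain eligible: "pembrolizumab treatment will be continued Q6W as per institutional guidelines until PD, unacceptable toxicity, or consent withdrawal by patient", up to 18 cycles.

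**The concern.** Two adjacent sentences in Section 3.1.2 use different clocks. They give the same result only while both drugs stop at about the same time. They separate in two situations that the protocol allows or makes possible.

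First, a patient who stops CyPep-1 and stays on pembrolizumab reaches day 30 after CyPep-1 while still being dosed. The visit meant to close safety observation then happens during treatment. Second, pembrolizumab is infused before CyPep-1 on shared dosing days. A patient who gets the first infusion and is never injected is in the Safety Analysis Set but outside the visit rule.

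At stake are scheduled measurements near the end of the AE window. TEAEs and changes in vital signs and laboratory values are primary endpoints in Phase 1b and secondary in Phase 2a. Section 8.8 schedules vital signs only at screening, Visit 1 of each cycle, EoT and Safety Follow-up, so misplacing the last of these removes the day-30 reading. Some patients reach the pembrolizumab-alone group through toxicity: Section 5.5.3.3 lists reactions that end CyPep-1 permanently and allows pembrolizumab monotherapy to be considered after toxicity attributed to CyPep-1 or the combination.

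A smaller matter is Section 5.6.4: "Medications and therapies taken within 28 days prior to the Screening Visit until the Safety Follow-up Visit will be recorded in the eCRF". Read alone, this would close medication recording at the same misplaced visit.

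**Working it through.** The plan gives no figure to reproduce. The check is day arithmetic from its own anchors, with the first dose on day 1.

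Formulas:

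- Safety Follow-up Visit = last CyPep-1 day + 30 (Section 3.1.2)
- Close of AE/TEAE window = last day of either drug + 30 (Sections 3.1 and 8.1; SAP 3.7.1)
- EoT = last day of either drug + 7 (±2), that is + 5 to + 9 (Section 4.5.3)
- Pembrolizumab day in cycle k = 1 + 42 × (k − 1), for k up to 18

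When pembrolizumab is the later drug, the shortfall is (last pembrolizumab + 30) − (last CyPep-1 + 30) = last pembrolizumab − last CyPep-1.

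1. **Both drugs stop together.** CyPep-1 is given every 2 weeks and pembrolizumab every 6 weeks, so the last CyPep-1 dose falls on or after the last pembrolizumab day, apart from the 3-day pembrolizumab window. There is essentially no shortfall.
2. **Illustration: CyPep-1 ends on day 15 and pembrolizumab continues to Cycle 4.** Pembrolizumab falls on days 1, 43, 85 and 127.
   - Visit: 15 + 30 = day 45.
   - Window closes: 127 + 30 = day 157.
   - The visit precedes the last dose by 127 − 45 = 82 days and the close of the window by 157 − 45 = 112 days, which equals 127 − 15.
3. **Extreme: one CyPep-1 dose on day 1 and pembrolizumab to Cycle 18.**
   - Visit: 1 + 30 = day 31, before the second infusion on day 43.
   - Last infusion: 1 + 17 × 42 = day 715. Window closes: day 745.
   - Shortfall: 745 − 31 = 714 days.
4. **Pembrolizumab but no CyPep-1.** The formula has no input, so no visit is required.

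In cases 2 to 4, EoT is the safety visit left after the last pembrolizumab dose. At day 5 to 9 it leaves 30 − 9 = 21 to 30 − 5 = 25 days, or 21/30 = 70% to 25/30 = 83% of the window. If EoT is held after day 30, the remainder is zero.

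With the visit at last dose of either drug + 30, the shortfall is zero in every pattern, and case 4 gains a visit.

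**The case against.** A reader might infer that these patients have no visit at all in the 30-day window. The documents do not support that. EoT follows the last dose of either drug and, at day 7 (±2), lies inside the window. Section 8.1 asks for AE assessment at every visit. The recording duties, 30 days for AEs and 90 for serious AEs, do not depend on the Safety Follow-up Visit, and SAP Section 3.7.1 describes AE capture through study completion.

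Other provisions narrow the gap further:

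- The 7-day EoT timing appears only in the sentence on premature withdrawal. If stopping is decided at the next cycle visit (an assumption), EoT falls about 42 days after the last infusion and spans the window.
- Patients without confirmed progression or new anti-cancer therapy keep 8-weekly tumor assessments. In case 2 these fall on days 57, 113 and 169, and day 169 is 169 − 157 = 12 days after the window closes, so earlier events could be elicited then. Sections 8.10 and 8.11 add examination, weight and performance status at site visits. These assessments are not designed as safety visits, and they stop at confirmed progression. The 3-monthly calls are described for survival only.
- For immune-related AEs both drugs are held, and unresolved toxicity ends both (Section 5.5.3.3). Not every toxicity stop therefore leads to pembrolizumab alone.

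A reader might also argue that immune-related events arising months after the last dose would be lost. Section 5.5.3.3 warns of them, but they lie beyond a 30-day window and a day-30 visit would not catch them either.

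The medication point is largely answered. The next sentence of Section 5.6.4 extends recording across the study, and SAP Section 3.3.7 counts concomitant use to 30 days after the last study treatment, although it opens with the same visit-based limit.

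Finally, the Appendix A table is absent from the available text and may time the visit differently. If so, it conflicts with Section 3.1.2 and the two still need reconciling. The difference in clocks stands after all of this.

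**Conclusion.** The concern holds as an inconsistency of modest consequence. The Safety Follow-up Visit follows CyPep-1 alone; the AE/TEAE window, the Safety Analysis Set, EoT and the skip rule follow either drug. For patients who continue pembrolizumab, the visit comes early by the interval between the two last doses (112 days in the illustration, at most 714). Patients given only pembrolizumab have no such visit. Where EoT is held at day 7 (±2), 21 to 25 of the 30 days have no required safety visit.

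The likely effect is less complete late TEAE, laboratory and vital-sign data in a small subset. One might infer that late AE rates are biased downward. That is plausible, but the documents give nothing to quantify it, and the continuing recording duties work against it. No efficacy analysis is affected.

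This rests on reading study treatment as either drug and on Appendix A not overriding Section 3.1.2. The number of affected patients is unknown. SAP Section 1 reports termination after Phase 1b, so it may be very few or none; with six patients planned, one would be 1/6 = 17%.

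**What to change.** Reconcile Section 3.1.2, the synopsis and Appendix A with Sections 3.1, 4.5.1, 4.5.3 and 8.1 and SAP Section 3.7.1. Apply the Safety Follow-up Visit to everyone in the Safety Analysis Set and time it 30 days after the last dose of study treatment, whichever drug is later. This matches the AE window and the skip rule already in the protocol. Align the opening sentence of Section 5.6.4 with the 30-day limit that SAP Section 3.3.7 uses for concomitant medication.

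The cost is about one amended sentence in each place, a later date for the same visit in patients who continue pembrolizumab, and one added visit for any patient who received only pembrolizumab.

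If amendment no longer serves a purpose after termination, the clinical study report should identify each patient whose last pembrolizumab dose fell after the Safety Follow-up Visit, or who never received CyPep-1. For each, it should give the date of the last safety assessment relative to the last dose.
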